9.1. Safety Parameters

9.1.1. Definition of Adverse Events (AE)

An adverse event is the development of an undesirable medical condition (other than progression of the malignancy under evaluation) or the deterioration of a pre-existing medical condition following or during exposure to a pharmaceutical product, whether or not considered causally related to the product. An undesirable medical condition can be symptoms (eg, nausea, chest pain), signs (eg, tachycardia, enlarged liver) or the abnormal results of an investigation (eg, laboratory findings, electrocardiogram). In clinical studies, an AE can include an undesirable medical condition occurring at any time, including run-in or washout periods, even if no study treatment has been administered.

The term AE is used to include both serious and non-serious AEs.

9.1.2. Definition of Serious Adverse Event (SAE)

A serious adverse event is an AE occurring during any study phase (i.e., screening, run-in, treatment, wash-out, follow-up), at any dose of the study drugs that fulfils one or more of the following criteria:

- Results in death
- Is immediately life-threatening
- Requires in-patient hospitalization or prolongation of existing hospitalization
- Results in persistent or significant disability or incapacity
- Is a congenital abnormality or birth defect in offspring of the subject
- Is an important medical event that may jeopardize the patient or may require medical intervention to prevent one of the outcomes listed above:
- Medical or scientific judgment should be exercised in deciding whether expedited reporting is appropriate in this situation. Examples of medically important events are intensive treatment in an emergency room or at home for allergic bronchospasm, blood dyscrasias, or convulsions that do not result in hospitalizations; or development of drug dependency or drug abuse.

The causality of SAEs (their relationship to all study treatment/procedures) will be assessed by the investigator(s) and communicated to AstraZeneca.

Adverse Events (AEs) for malignant tumours reported during a study should generally be assessed as Serious AEs. If no other seriousness criteria apply, the 'Important Medical Event' criterion should be used. In certain situations, however, medical judgement on an individual event basis should be applied to clarify that the malignant tumour event should be assessed and reported as a Non-Serious

18 November 2020 Page **98** of **164**

AE. For example, if the tumour is included as medical history and progression occurs during the study, but the progression does not change treatment and/or prognosis of the malignant tumour, the AE may not fulfill the attributes for being assessed as Serious, although reporting of the progression of the malignant tumor as an AE is valid and should occur. Also, some types of malignant tumours, which do not spread remotely after a routine treatment that does not require hospitalization, may be assessed as Non-Serious; examples include Stage 1 basal cell carcinoma and Stage 1A1 cervical cancer removed via cone biopsy. The above instruction applies only when the malignant tumour event in question is a new malignant tumour (i.e., it is not the tumour for which entry into the study is a criterion and that is being treated by the IP under study and is not the development of new or progression of existing metastasis to the tumour under study). Malignant tumours that — as part of normal, if rare, progression — undergo transformation (e.g., Richter's transformation of B cell chronic lymphocytic leukemia into diffuse large B cell lymphoma) should not be considered a new malignant tumour.

9.1.3. Definition of Adverse Events of Special Interest (AESI)

An adverse event of special interest (AESI) is one of scientific and medical interest specific to understanding of the Investigational Product and may require close monitoring and rapid communication by the investigator to the sponsor. An AESI may be serious or non-serious. The rapid reporting of AESIs allows ongoing surveillance of these events in order to characterize and understand them in association with the use of this investigational product.

AESIs for durvalumab ± tremelimumab include but are not limited to events with a potential inflammatory or immune-mediated mechanism and which may require more frequent monitoring and/or interventions such as steroids, immunosuppressants and/or hormone replacement therapy. These AESIs are being closely monitored in clinical studies with durvalumab monotherapy and combination therapy. An immune-mediated adverse event (imAE) is defined as an AESI that is associated with drug exposure and is consistent with an immune-mediated mechanism of action and where there is no clear alternate etiology. Serologic, immunologic, and histologic (biopsy) data, as appropriate, should be used to support an imAE diagnosis. Appropriate efforts should be made to rule out neoplastic, infectious, metabolic, toxin, or other etiologic causes of the imAE.

<< The following should be added if applicable. In the event of imAE or suspected imAE, the AstraZeneca study team may request relevant clinical information (including images) for those subjects who demonstrate the event, and may request the independent review by external experts based on the acquired clinical information.>>

If the Investigator has any questions in regards to an event being an imAE, the Investigator should promptly contact the Study Physician.

AESIs observed with durvalumab ± tremelimumab include:

- Diarrhea/Colitis and intestinal perforation
- Pneumonitis/ ILD

18 November 2020 Page **99** of **164**

- Hepatitis/ transaminase increases
- Endocrinopathies (i.e., events of hypophysitis/hypopituitarism, adrenal insufficiency, hyperand hypothyroidism, and type I diabetes mellitus)
- Rash/Dermatitis
- Nephritis/ Blood creatinine increases
- Pancreatitis/ serum lipase and amylase increases
- Myocarditis
- Myositis/ Polymyositis
- Neuropathy/ neuromuscular toxicity (e.g. Guillain-Barré, and myasthenia gravis)
- Intestinal Perforation

Other inflammatory responses that are rare/less frequent with a potential immune-mediated etiology include, but are not limited to:

- Pericarditis
- Sarcoidosis
- Uveitis
- Other events involving the eye and skin
- Hematological events
- Rheumatological events
- Vasculitis
- Non-infectious meningitis
- Non-infectious encephalitis

It is possible that events with an inflammatory or immune mediated mechanism could occur in nearly all organs.

In addition, infusion-related reactions and hypersensitivity/anaphylactic reactions with a different underlying pharmacological aetiology are also considered AESIs.

Further information on these risks (e.g., presenting symptoms) can be found in the current version of the durvalumab and tremelimumab Investigator's Brochures. More specific guidelines for their evaluation and treatment are described in detail in the Dosing Modification and Toxicity Management Guidelines (see Appendix 1). These guidelines have been prepared by the Sponsor to assist the Investigator in the exercise of his/her clinical judgment in treating these types of toxicities. These guidelines apply to AEs considered causally related to the study drug/study regimen by the reporting investigator.

18 November 2020 Page **100** of **164**

9.1.4. Thoracic Radiation Adverse Events of Special Interest

Esophagitis

Inflammation of the esophagus can happen as a recognized adverse event with thoracic radiation. Diagnostic workup and management is outlined in Appendix 8.

Radiation-related Toxicities

Adverse events associated with therapeutic radiation will be graded weekly and coded using common terminology criteria for adverse events CTCAE 4.03 definitions. Treatment management will be determined by grade of toxicity using the treatment modifications listed in Appendix 7.

9.1.5. Immune-related Adverse Events

Based on the mechanism of action of durvalumab and tremelimumab leading to T-cell activation and proliferation, there is a possibility of observing irAEs during the conduct of this study. Potential irAEs may be similar to those seen with the use of ipilimumab, BMS-936558 (anti-PD-1 mAb), and BMS-936559 (anti-PD-L1 mAb) and may include immune-mediated enterocolitis, dermatitis, hepatitis (hepatotoxicity), pneumonitis, and endocrinopathies^{12, 24, 28}. These AEs are inflammatory in nature and can affect any organ. With anti-PD-L1 and anti-CTLA-4 combination therapy, the occurrence of overlapping or increasing cumulative toxicities that include irAEs could potentially occur at higher frequencies than with either durvalumab or tremelimumab monotherapy. Patients should be monitored for signs and symptoms of irAEs. In the absence of an alternate etiology (e.g., infection or PD), an immune-related etiology should be considered for signs or symptoms of enterocolitis, dermatitis, pneumonitis, hepatitis, and endocrinopathy. In addition to the dose modification guidelines provided in Table 1, it is recommended that irAEs are managed according to the general treatment guidelines outlined for ipilimumab⁹¹. These guidelines recommend the following:

- Patients should be evaluated to identify any alternative etiology.
- In the absence of a clear alternative etiology, all events of an inflammatory nature should be considered immune related.
- Symptomatic and topical therapy should be considered for low-grade events.
- Systemic corticosteroids should be considered for a persistent low-grade event or for a severe event.
- More potent immunosuppressives should be considered for events not responding to systemic steroids (e.g., infliximab or mycophenolate).
- If the Investigator has any questions in regards to an AE being an irAE, the Investigator should immediately contact the Study Physician.

18 November 2020 Page **101** of **164**

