1.6.2. Perioperative Systemic Therapy in Stage III NSCLC

A rational approach to eradicate micrometastatic disease and minimize the risk of relapse for patients with locally advanced NSCLC, is treatment with adjuvant or neoadjuvant chemotherapy. Many adjuvant studies have been performed and these trials are summarized in Table 1.

Although there are some conflicting results, the overall evidence from these studies suggests that adjuvant platinum doublet chemotherapy is beneficial for good performance status patients with stage II-IIIA disease³⁶⁻⁴¹. The LACE meta-analysis of modern adjuvant and neoadjuvant trials, all of which used cisplatin-based chemotherapy, suggested a 5% survival advantage at 5 years from adjuvant chemotherapy with the benefit

18 Nov 2020 Page **42** of **164**

being greatest for stage II and IIIA patients. A 2010 meta-analysis including both older and more recent trials confirmed the survival benefit shown in the LACE meta-analysis and suggested a benefit of adjuvant chemotherapy for stage IB disease patient^{42, 43}

TABLE 1: SELECTED NSCLC STUDIES OF ADJUVANT CHEMOTHERAPY

Trial	Stage	Treatment	n	5 year OS	HR	p-value
ALPI	1-111	Surgery	603	45%	0.96	0.59
		MVP	601	50%		
IALT	1-111	Surgery	935	40%	0.86	<0.03
		Cisplatin-	932	44.5%		
		based				
ANITA	IB-IIIA	Surgery	433	43%	0.80	0.017
		Cisplatin+	407	51%		
		Vinorelbine				
BLT	I-IIIA	Surgery	189	58%	1.02	0.90
		Cisplatin-	192	60%		
		based				
NCIC/JBR10	IB-II	Surgery	240	54%	0.69	0.03
		Cisplatin+	242	69%		
		Vinorelbine				
CALGB	IB	Surgery	171	57%	0.80	0.10

18 Nov 2020 Page **43** of **164**

	Carboplatin+	173	59%	
	Paclitaxel			

OS= overall survival, HR= hazard ratio, ALPI: Adjuvant Lung Cancer Project Italy, IALT= International Adjuvant Lung Cancer Trial, ANITA= Adjuvant Navelbine Trialist Association, BLT= Big Lung Trial, NCIC= National Cancer Institute Canada, CALGB: Cancer and Leukemia Group, MVP= Mitomycin, Vindesine, Cisplatin.

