6.3. Definition of Dose Limiting Toxicity (DLT)

Dose-limiting toxicities (DLTs) will be evaluated from the first day of administration of durvalumab (cohort 1) or durvalumab+tremelimumab (cohort 2), in this trial. The period for evaluating DLTs will be from the day of first administration of study therapy until 30 days after surgical resection or 100 days following the last dose of study therapy, whichever occurs later. Subjects who do not remain on the study up to this time for reasons other than DLT will be replaced with another subject. Grading of DLTs will follow the guidelines provided in the Common Terminology Criteria for Adverse Events (CTCAE) version 4.0. A patient who experiences a DLT will be permanently discontinued from treatment and will proceed to surgery after standard preoperative evaluation by a surgeon and anesthesiologist. Prior to surgery any treatment related toxicity should have resolved to ≤grade 1. [5]

A DLT will be defined as any Grade 3 or higher toxicity that occurs during the DLT evaluation period. Toxicity that is clearly and directly related to the primary disease or to another etiology is excluded from this definition. The following will be DLTs:

- Any Grade 4 irAE
- Any ≥ Grade 3 colitis
- Any Grade 3 or 4 non-infectious pneumonitis irrespective of duration
- Any Grade 2 pneumonitis that does not resolve to ≤ Grade 1 within 3 days of the initiation of maximal supportive care
- Any Grade 3 irAE, excluding colitis or pneumonitis, that does not downgrade to Grade 2 within 3
 days after onset of the event despite optimal medical management including systemic
 corticosteroids or does not downgrade to ≤ Grade 1 or baseline within 14 days
- Liver transaminase elevation > 8 × ULN or total bilirubin > 5 × ULN
- Any ≥ Grade 3 non-irAE, except for the exclusions listed below

The definition excludes the following conditions:

- Grade 3 fatigue lasting ≤ 7 days
- Grade 3 endocrine disorder (thyroid, pituitary, and/or adrenal insufficiency) that is managed
 with or without systemic corticosteroid therapy and/or hormone replacement therapy and the
 subject is asymptomatic
- Grade 3 inflammatory reaction attributed to a local antitumor response (e.g., inflammatory reaction at sites of metastatic disease, lymph nodes, etc.)
- Concurrent vitiligo or alopecia of any AE grade
- Grade 3 infusion-related reaction (first occurrence and in the absence of steroid prophylaxis) that resolves within 6 hours with appropriate clinical management

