- Whether specific immune-mediated events (and/or laboratory indicators of such events) are noted in these guidelines or not, patients should be thoroughly evaluated to rule out any alternative etiology (e.g., disease progression, concomitant medications, and infections) to a possible immunemediated event. In the absence of a clear alternative etiology, all such events should be managed as if they were immune related. General recommendations follow.
- Symptomatic and topical therapy should be considered for low-grade (Grade 1 or 2, unless otherwise specified) events.
- For persistent (>3 to 5 days) low-grade (Grade 2) or severe (Grade ≥3) events, promptly start prednisone 1 to 2 mg/kg/day PO or IV equivalent.
- Some events with high likelihood for morbidity and/or mortality - e.g., myo-carditis, or other similar events even if they are not currently noted in the guidelines – should progress rapidly to high dose IV corticosteroids (methylprednisolone at 2 to 4 mg/kg/day) even if the event is Grade 2, and if clinical suspicion is high and/or there has been clinical confirmation. Consider, as necessary, discussing with the study physician, and promptly pursue specialist consultation.
- If symptoms recur or worsen during corticosteroid tapering (28 days of taper), increase the corticosteroid dose (prednisone dose [e.g., up to 2 to 4 mg/kg/day PO or IV equivalent]) until stabilization or improvement of symptoms, then resume corticosteroid tapering at a slower rate (>28 days of taper).
- More potent immunosuppressives such as TNF inhibitors (e.g., infliximab; also refer to the individual sections of the imAEs for specific type of immunosuppressive) should be considered for events not responding to systemic steroids. Progression to use of more potent immunosuppressives should proceed more rapidly in events with high likelihood for morbidity and/or mortality - e.g., myocarditis, or other similar events even if they are not currently noted in the guidelines

18-Nov-2020 Page 125 of 164

Grade 4

IND #134339

Dosing Modification and Toxicity Management Guidelines (TMGs) for Durvalumab Monotherapy, Durvalumab in Combination with other Products, or Tremelimumab Monotherapy 17 November 2020 Version (CTCAE v4.03)

General Considerations regarding Immune-Mediated Reactions

Dose Modifications

Permanently discontinue study drug/study regimen.

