over baseline per	resolution to		volume and maintain hydration.	
day;	Grade ≤1; study	_	Urgent GI consult and imaging	
Grade 4 Diarrhea:	drug/study	_	and/or colonoscopy as appropriate.	
life threatening	regimen can be	_	If still no improvement within 2 days continue steroids and	
consequences)	resumed after		promptly add further	
(Grade 3 Colitis:	completion of		immunosuppressives (e.g., infliximab at 5 mg/kg IV, may be	
severe abdominal	steroid taper.		repeated at 2 and 6 weeks after	
pain, change in	Permanently		initial dose at the discretion of the	
bowel habits,	discontinue		treating provider). Caution : Ensure GI consult to rule out bowel	
medical	study drug/study		perforation and refer to infliximab	
intervention	regimen for		label for general guidance before using infliximab. If perforation is	
indicated,	Grade 3 if		suspected, consult a surgeon	
peritoneal signs;	toxicity does not improve to		experienced in abdominal surgery	
Grade 4 Colitis:	Grade ≤1 within	_	immediately without delay.	
life-threatening	14 days.	_	Once the patient is improving, gradually taper steroids over ≥28	
consequences,	•		days and consider prophylactic	
urgent	-Permanently discontinue		antibiotics, antifungals, and anti- PJP treatment (refer to current	
intervention	discontinue study drug for		NCCN guidelines for treatment of	
indicated)	1) Grade 3 colitis in			

Page **133** of **164** 18-Nov-2020

IND #134339

	(Grade 3 Perforation: severe symptoms, elective* operative intervention indicated; Grade 4 Perforation: life- threatening consequences, urgent intervention indicated)	patients treated with CTLA-4 inhibitors or 2) Any grade large intestine perforation/Intestinal perforation in any patient treated with ICI. Grade 4 Permanently discontinue study drug/study regimen.	cancer-related infections [Category 2B recommendation]). ^a
	*This guidance anticipates that Grade 3 operative interventions of perforations are usually not elective		
Hepatitis (elevated LFTs) Infliximab should not be used for management of immune-related hepatitis.	Any Elevations in AST, ALT or TB as Described Below	General Guidance	 For Any Elevations Described: Monitor and evaluate liver function test: AST, ALT, ALP, and TB. Evaluate for alternative etiologies (e.g., viral hepatitis, disease progression, concomitant medications).

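### Section 9.1.5 gives general irAE guidance that names infliximab with no hepatitis exception and no link to Appendix 1, which excludes infliximab for immune hepatitis; its Table 1 pointer is also wrong

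*Combined protocol and SAP*

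**What the plan says.** Section 9.1.5 (Immune-related Adverse Events) puts hepatitis within its scope: where no other cause is found, "an immune-related etiology should be considered for signs or symptoms of enterocolitis, dermatitis, pneumonitis, hepatitis, and endocrinopathy". It then gives its management basis: "In addition to the dose modification guidelines provided in Table 1, it is recommended that irAEs are managed according to the general treatment guidelines" set out for ipilimumab. A short list follows. Systemic corticosteroids are to be considered for low-grade events that persist and for severe ones. The next step is: "More potent immunosuppressives should be considered for events not responding to systemic steroids (e.g., infliximab or mycophenolate". No organ is excepted, and Appendix 1 is not mentioned.

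Sections 6.4.1 and 9.1.3 both send the reader to the Dosing Modification and Toxicity Management Guidelines in Appendix 1 (section 17). In the hepatitis block those guidelines say: "Infliximab should not be used for management of immune-related hepatitis". The statement is repeated in the row for higher liver-enzyme or bilirubin elevations, for patients who have not improved on intravenous methylprednisolone; the agent named there is mycophenolate mofetil. On steroids, the general considerations of Appendix 1 say that for persistent grade 2 or "severe (Grade ≥3) events, promptly start prednisone 1 to 2 mg/kg/day PO or IV equivalent".

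The only Table 1 in the document is in section 1.6.2: "TABLE 1: SELECTED NSCLC STUDIES OF ADJUVANT CHEMOTHERAPY".

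**The concern.** Section 9.1.5 carries the title a physician would look for when an immune-related event occurs, and it reads as self-contained. Someone who opens it for a hepatitis that steroids have not controlled finds infliximab offered as one of two examples, no exception for the liver, and a reference for dosing rules that ends in a literature table. Nothing in the section says that another part of the protocol excludes infliximab in this situation.

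What is at stake is patient safety and uniform conduct. A patient could receive a rescue treatment that the protocol's own toxicity guideline excludes for that event. Section 6.1.2 also allows for one or two further sites, so two physicians could handle the same event differently and each believe that the protocol was followed.

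**Working it through.** No arithmetic applies: the point depends on no rate, sample size or error probability. The check sets the texts side by side.

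1. **Scope.** Section 9.1.5 lists hepatitis twice: among the irAEs that may occur, and among those for which an immune cause should be considered. Its recommendations apply to irAEs in general, so hepatitis falls under them by scope. No sentence there pairs infliximab with hepatitis.

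2. **Rescue after steroid failure.** Section 9.1.5 offers infliximab or mycophenolate as examples, for any organ. Appendix 1 excludes infliximab for immune-related hepatitis, stating this both in the label of the hepatitis block and in the steroid-refractory step, where it names mycophenolate mofetil. The two texts overlap on mycophenolate and diverge on infliximab.

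3. **General wording inside Appendix 1.** The general considerations of Appendix 1 contain a sentence much like the one in 9.1.5, also giving infliximab as an example for events that steroids do not control. That sentence directs the reader to the sections on individual events for the type of immunosuppressive, and so to the hepatitis exclusion. Section 9.1.5 has no such direction.

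4. **Start of steroids.** For persistent low-grade or severe events, 9.1.5 asks that steroids be considered. For persistent grade 2 or grade 3 and higher events, Appendix 1 asks for a prompt start and gives a dose range. The strength of the instruction differs.

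5. **Pointer.** Section 9.1.5 locates the dose-modification guidance in Table 1. The table in section 1.6.2 and the entry in the List of Tables both show that Table 1 is a summary of adjuvant chemotherapy trials with no dosing rule for this study. Section 6.4.1 locates the guidance in Appendix 1.

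6. **Order of precedence.** Section 9.1.3 describes Appendix 1 as the more specific guidance. It also says that the guidelines are there to assist the investigator's clinical judgment. Section 9.1.5 states no order between its own list and Appendix 1.

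Steps 2, 3 and 5 together show the gap: a general sentence without the exception found elsewhere, and no working link to the place where the exception stands.

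**The case against.** The strongest reply is that the texts do not collide. Section 9.1.5 is worded as a recommendation, gives alternatives, and one of them is the agent that Appendix 1 names for refractory hepatitis. An investigator can satisfy both texts. Appendix 1's own general sentence is nearly identical, and 9.1.3, two sections before 9.1.5, calls Appendix 1 the more specific guidance, so a careful reader would let it govern. All of this stands. It rules out reading the passages as two orders that cannot both be obeyed. It does not close the gap, because 9.1.5 neither repeats that hierarchy nor leads to Appendix 1.

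A reader might also infer that the difference on steroids distorts the co-primary safety endpoint. Section 6.3 counts certain grade 3 irAEs as DLTs if they have not downgraded to grade 2 within 3 "days after onset of the event despite optimal medical management including systemic" corticosteroids, or to grade 1 or baseline within 14 days. One could then add that a single reclassified DLT is 1/16 = 6.25 percentage points. Under the Beta(0.05, 0.95) prior in section 12.2.2, the posterior probability of a rate above 25% is 0.339 at 1 of 4 and 0.755 at 2 of 4, against the 70% threshold.

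The documents do not support that inference:

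- Transaminases above 8×ULN or bilirubin above 5×ULN are listed as DLTs whatever treatment is given.
- Grade 3 or higher colitis, grade 3 or 4 pneumonitis and grade 4 irAEs carry no steroid condition, and asymptomatic managed grade 3 endocrine disorders are excluded.
- For the remaining grade 3 irAEs, section 6.3 already names systemic corticosteroids as part of management. Timing could matter in principle because the 3-day clock runs from onset, but nothing shows that the difference in wording would change a classification.
- The figures describe any single reclassified DLT from any cause. They do not measure an effect of 9.1.5.

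**Conclusion.** The point holds as an internal inconsistency in safety guidance. Section 9.1.5 lacks the hepatitis exception that Appendix 1 states, differs from it on how firmly steroids are to be started, and cites the wrong table for dose modification. A reader relying on 9.1.5 alone could depart from Appendix 1. This is more than clerical, because the missing exception concerns rescue treatment.

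Its reach is every patient in both cohorts, planned at 16 evaluable patients each; its practical effect is confined to immune-related events needing steroids and, for infliximab, to hepatitis that steroids do not control. The documents give no expected number of such events, so no count or rate is offered. No effect on DLT classification, the stopping rule or the primary analysis is claimed.

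The conclusion rests on two readings: that hepatitis falls under the 9.1.5 recommendations by the section's scope, and that Appendix 1 is the guideline meant by 6.4.1 and 9.1.3. It takes no position on which clinical rule is right.

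**What to change.** Reconcile section 9.1.5 with Appendix 1 on rescue treatment after steroid failure and on the start of steroids, and state in 9.1.5 which text governs where they differ. Replace the reference to Table 1 with the correct location of the dose-modification guidance, which section 6.4.1 gives as Appendix 1. The clinical content of the reconciled text is for the sponsor and the investigator to settle.

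The cost is a wording change in an amendment, with the IRB approval that section 13.4 requires. No procedure, visit or patient is added.
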